**Up and Down: Use of Dynamic Partial Body Weight Support
Play Environment to Encourage Upright Mobility and
Exploration in Infants with Down Syndrome (DS)**

NCT number:

Date:1/06/2022

Research objective

Children with Down syndrome (DS) experience delayed mobility, which decreases their opportunity for exploration and impacts the development of their cognitive, communication, and social-emotional skills. Physical therapy interventions for infants with DS frequently focus on the development of postural control and body weight support to enhance the development of motor skills. Partial body weight supported (PWBS) intervention, where part of the child's body weight is offloaded through the use of a harness and allows for easier movement through space, is an effective intervention for infants with DS, leading to earlier onset of independent mobility and increased physical activity. We are combining PWBS support for infants with DS who are not yet walking, within an enriched play environment to better understand how PWBS may impact their mobility, exploration, and overall activity level.

Research Design

This is a randomized, crossover pilot study design with the sampled children serving as their own controls

Methods

Participants will include children of all genders, with Down Syndrome (any form) diagnosis, under 36 months of age, able to sit independently and one parent or legal guardian of all genders ages 18 and above. Inclusion criteria for the study: 1) The child will have a medical diagnosis of DS (any form); 2) be under 36 months old; 3) able to sit independently; 4) one parent must be able to read proficiently enough in English to complete a written assessment. Children will be excluded from the study if: 1) they can walk independently; 2) have uncontrolled seizures; 3) have known medical precautions that would prohibit them from wearing a harness; 4) have other developmental disability diagnoses. Participants will be recruited by the research team via social media postings, emails to known rehabilitation professionals in the Seattle region, and via fliers hung-up and passed out at local healthcare clinics and hospitals. The research team will also send emails to past research participants who had shared their email address and had agreed to be contacted for future studies. Potential participants will self-elect to call or email the research team to hear more about the study to determine whether or not they are interested in participating. Interested potential participants would then be screened for eligibility by a member of the research team.

We will conduct our work in this pilot study using a randomized, crossover design with children serving as their own controls. Study activities for each child will take place over 9 weeks in the PI's research lab on UW campus (CHDD buildings). After successful recruitment, children baseline assessment will be conducted during week one. On the first visit, parents will be asked to review and sign informed consent documentation to participate and baseline assessments will be completed. Then randomization assignment into 2 groups for intervention either play sessions using the PBWS (harness) or control play group (no harness, 3 sessions per week) for 3 weeks (weeks 2-4 of the study and weeks 6-8), with a washout and reassessment period during week 5 prior to crossover. A final reassessment session will be done during week 9.

Figure 1. (Left) Portable PUMA system for Partial Body Weight Support in an Enriched Environment; **(Right)** Close up photo of the harness attachment and portable frame components.

Equipment: Each child will be introduced to an 81 square foot play environment with dynamic enrichment (PEDE). The PEDE will consist of a **Portable Mobility Aid for Children (PUMA) system and a PBWS harness** that offers 1, 2, 4, or 8 lb counterweighting (Enliten, Newark, DE, USA, images of the system at <https://www.enlitenllc.com/puma.html>) as well as toys and toy placement that facilitates upright exploration. A **standardized set of toys and equipment** will be used at each site for consistency. The **PEDE** will be set up over bi-colored 12" x 12" interlocking floor tiles to provide a firm yet padded play surface and also allow for straightforward measurement of movement trajectories across the play space. Standardized toys will include but not be limited to a set of four nesting benches, a crawl-in play cube, a manipulative activity cube that can be accessed in seated or standing positions, cause and effect toys, and sensory play items such as a Montessori Busy Board. (See Appendix B for photos of proposed standardized toys).

In the control condition, children will be placed in the PEDE but not attached to the PUMA or harness. In the experimental condition, children will be placed in the harness and attached to the PUMA, which acts as a partial body weight support. In both conditions, the children will be placed in sitting initially, and though the researchers will encourage the children to stand through placement of toys and verbal/visual cues, position changes will not be imposed by researchers or caregivers. While in the PEDE, children will play for up to 30 minutes within a 60-minute appointment. Children will be given breaks as needed based on the following criteria: the child cannot be redirected, distracted, or calmed by parent/researcher for more than 1 min with repeated attempts to engage/distract; the child falls asleep; there is a safety concern or harness slippage; or the parent requests a break for their child. Once a child reaches 30 minutes of exposure to the PEDE or the 60-minute appointment time ends, the child's intervention session will end for the day. The amount of time in the harness and PUMA system will be documented at each study visit.

Dependent Measures:

Aim 1: Explore the effects of a harness-based intervention on exploratory behavior among infants with DS

Exploratory behavior expressed as activity counts during all intervention and control play sessions will be measured using **wrist and ankle mounted accelerometers (Actigraph GT3X+)**. These passive sensors will be placed on the child's right-side wrist and ankle and covered with wrist bands. The sensors will be

set to capture data in 1 second epochs. Each intervention session will be video recorded, and exploratory activity will also be coded from the recordings. Coding will be conducted using a momentary time sampling strategy from the videos of the first session of week 2 and week 6 (first exposure to the play environment in each condition) and the last session of week 4 and week 8 (last exposure to the play environment in each condition). Coding metrics will include physical activity, classified according to the Observational System for Recording Physical Activity in Children- Preschool version, social interactions, classified according to the **Code for Active Student Participation and Engagement-Revised (CASPER-III)**, and object-related actions, classified by whether a child is touching, holding, or using a portable object with their hands using a categorical yes/no binary. (See Appendix A for a detailed description of the behavioral coding scheme). Inter- and intra-rater reliability of at least 90% agreement will be established for each exploratory behavior on 10% of the video recordings using the ratio of [agreements/ (agreements + disagreements) X100] to establish a percentage of agreement.

Aim 2: Explore the effects of a harness-based intervention on gross motor skill acquisition among infants with DS

Standardized study assessments will occur at the initial study session, during week 5 (midpoint), and during week 9 (post-test). The **Gross Motor Function Measure-88 (GMFM)** will be used to assess gross motor development. Specifically, we will use sections D (Standing), and E, (Walking, Running & Jumping). The GMFM-88 is a reliable measurement tool and is valid for children with Down syndrome. The GMFM-88 will be administered by the site investigator but will be scored by a single, blinded, trained assessor via video recording.

Aim 3: Explore the effects of a harness-based intervention on parent-reported mastery motivation among infants with DS

Mastery motivation will be measured via parent report using the **Revised Dimensions of Mastery Questionnaire (DMQ-18) Infant version**. The DMQ-18 has one general competence scale and six mastery motivation scales including: cognitive/object persistence, gross motor persistence, social persistence with adults, social persistence with children/peers, mastery pleasure, and negative reactions to challenge in mastery situations. The test-retest reliability of parent ratings of children with typical development and cerebral palsy is good. The DMQ has been validated for children with DS.

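### For GMFM D/E, neither the allocation nor the analysis allows for entry motor stage, so a chance imbalance of stage between the two orders costs precision (not validity)

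*Protocol*

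**What the plan says.** **Entry.** Protocol, Methods: a child must be "able to sit independently" and is excluded if "they can walk independently". The age criterion is "be under 36 months old", with no lower limit.

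**Allocation.** Also in Methods, "children baseline assessment will be conducted during week one". Order is assigned after that: "Then randomization assignment into 2 groups for intervention either play sessions using the PBWS (harness) or control play group". No ratio, block size, stratification or minimisation factor is given in either document.

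**Motor outcome.** Protocol, Dependent Measures, Aim 2: GMFM-88 sections D and E are assessed at the first session, in week 5 and in week 9. A single blinded assessor scores them from video.

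**Analysis.** SAP, Data Analysis: raw D and E scores after control are compared with those after harness by a paired t-test at alpha 0.05, with a rank test if the data are not normal. The model has no term for period, order, baseline score or motor stage. The SAP is headed as covering power but gives no sample size, SD, target effect or expected gain.

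**The concern.** Using each child as its own control removes the child's starting level. It does not remove what the child gains unaided between the two post-tests, about four weeks apart. That gain enters the harness-minus-control difference with a plus sign in control-first children and a minus sign in harness-first children.

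Sections D and E score standing and walking skills. A child who only sits has little scope to score in four weeks; one already pulling to stand may have much more. If gain does depend on entry stage, and one order happens to hold more children near standing, the excess gain goes into the estimated harness effect. In a small pilot such imbalance is common. Stage can be observed at the week 1 visit, before order is assigned, so this part of the error could be avoided cheaply.

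**Working it through.** There is no planned figure to reproduce. The algebra is exact; the sizes rest on assumptions.

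**Inputs from the documents.** Post-tests in weeks 5 and 9; two orders; paired t-test; alpha 0.05 (taken as two-sided).

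**Assumed inputs.** Half the children in each of two stages; equal orders; total N of 10 or 12 for illustration; D/s from 0 to 2.

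**1. Where the error comes from.** Let g be a child's natural gain from week 5 to week 9 and τ the condition effect. Apart from noise, the week 9 minus week 5 change is g + τ in control-first children and g − τ in harness-first children. Half the difference between the order means is

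τ + (mean g in control-first − mean g in harness-first)/2.

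With equal orders, the average harness-minus-control difference behind the paired t-test is the same quantity. A common period term would remove the average gain but not this second part.

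**2. How often stage is unbalanced.** N = 12, six faster-stage children, six children per order, stage ignored at allocation:
- 4:2 split or worse: 1 − 400/924 = 0.57. A 4:2 split shifts the estimate by (4/6 − 2/6) × D/2 = D/6.
- 5:1 or worse: (72 + 2)/924 = 0.08. A 5:1 split shifts it by (5/6 − 1/6) × D/2 = D/3.

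In raw points at N = 10, with D assumed to be 10 (or 4): a 4:1 split or worse has probability 52/252 = 0.206. The error at 4:1 is 0.6 × 10/2 = 3 points (0.6 × 4/2 = 1.2), and the SD of the error is 0.333 × 10/2 = 1.67 points (0.333 × 4/2 = 0.67). Without a residual SD, these cannot be called large or small, so the next step is scale-free.

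**3. Precision.** The variance of the estimate is (s² + D²/4)/N when stage is ignored and s²/N when it is balanced and modelled. The share removed is (D²/4)/(s² + D²/4).

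| D/s | Variance removed | SE ratio, ignored to modelled | Equivalent multiple of N |
|---|---|---|---|
| 0 | 0% | 1.00 | 1.00 |
| 0.5 | 6% | 1.03 | 1.06 |
| 1 | 20% | 1.12 | 1.25 |
| 1.5 | 36% | 1.25 | 1.56 |
| 2 | 50% | 1.41 | 2.00 |

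At N = 12 the SD of the estimate falls from √(1.25/12) s = 0.32s to √(1/12) s = 0.29s at D/s = 1, and from √(2/12) s = 0.41s to 0.29s at D/s = 2.

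**4. Simulated power.** N = 12, six per order, true effect 0.8s, slower-stage gain 1s.

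| Allocation and analysis | D/s = 1 | D/s = 2 |
|---|---|---|
| Unstratified, planned paired t-test | 0.13 | 0.04 |
| Stratified, stratum main effect added to the harness-minus-control difference | 0.08 to 0.09 | below 0.01 |
| Unstratified, change on order only | 0.60 | 0.40 |
| Unstratified, change on order and stage | 0.65 | 0.65 |
| Stratified, change on order and stage | about 0.69 | about 0.69 |

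The planned test's power depends on the average gain. With an average gain of 1s it is 0.34 and 0.25. The step from row 1 to row 3 comes from the missing period term; only the later steps come from motor stage.

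**5. Type I error.** Unstratified allocation with a period term stays near 0.05. With stratified allocation and stage left out of the model, at D/s = 2 it falls to 0.006 with a period term and 0.001 with the paired t-test (average gain 1s). The true error shrinks but the reported SE does not.

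**The case against.** **The size is assumed.** This stands. If gain does not depend on stage, the benefit is nil. At D/s = 0.5 and N = 12, adding stage without stratifying slightly lowers power (0.68 to 0.66), because it uses a degree of freedom. One binary factor would also not capture all variation in gain. The argument is made for GMFM D/E only; it is less clear for DMQ-18 and is not made for activity counts or coded behaviour.

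**The missing period term matters more.** This also stands. Under simple randomisation with D/s = 1, N = 12 and an average gain of 1s, the SD of the estimate is 0.42s with the planned test, 0.34s with a period term and 0.32s with period and stage. The remedy must therefore supply the period term as well.

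**Stratifying adds little once stage is modelled.** True: power is about 0.65 without it and 0.69 with it. But the plan does neither.

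**Stronger readings that the documents do not support.** A reader might infer that the harness effect is biased or the test invalid. Randomised order makes stage imbalance a matter of chance, and differences in starting level cancel within child. A reader might also infer that the team knew motor stage and chose to disregard it. The protocol says nothing of the randomisation method, so silence is all that can be reported. Nor is a GMFM score shown to exist at allocation, since scoring is done from video.

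**Conclusion.** The point holds as a low-severity improvement in precision for GMFM D/E. The wide entry range, the absence of any stated balancing factor and the unadjusted paired t-test are plain in the documents, and it follows algebraically that a difference in mean natural gain between orders enters the estimate at half its size.

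How much this matters cannot be settled from the documents. Over D/s from 0 to 2, with equal stages and equal orders, ignoring stage raises the SE by 0 to 41%. For an exploratory pilot that is worth a cheap correction. It does not put the trial's validity in doubt. Counting from the planned test, most of the recoverable power lies in the analysis, and part of that is owed to the period term rather than to motor stage.

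**What to change.** **Analysis (the main change).** For GMFM D/E, replace the paired t-test with a regression of each child's week 9 minus week 5 change on order and week 1 motor stage, or on order and the week 1 D/E score. Code control-first as 1 and harness-first as 0; half the order coefficient is the harness-minus-control effect. This is equivalent to fitting period and stage-by-period terms. A stratum main effect on the harness-minus-control difference will not do, because the gain changes sign with order. Like the planned test, the regression assumes no carry-over.

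**Allocation.** Randomise order in small permuted blocks within one two-level factor noted at the week 1 visit, for example whether the child pulls to stand or stands with support. Record it there and then, because GMFM is scored later. Do not stratify without also modelling order and stage: the test would then be too conservative.

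**Cost.** Two allocation lists in place of one, one item recorded at an existing visit, a possible one-child imbalance in an odd-sized stratum, and one or two degrees of freedom. No extra visit is needed. If only one change is made, make the analysis change.

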**Up and Down: Use of Dynamic Partial Body Weight Support
Play Environment to Encourage Upright Mobility and
Exploration in Infants with Down Syndrome (DS)**

NCT number:

Date: 1/06/2022

Statistical Design and Power

Data Analysis:

All statistical analyses will be conducted using SPSS (version 27.0 IBM, Armonk, NY). Descriptive participant characteristics (e.g., age, sex, race/ethnicity, DS type) will be summarized as categorical variables. The dependent variables for this study are exploratory behavior activity counts, exploratory behavior coding counts, GMFM sections D and E raw scores, and DMQ-18 raw scores. Descriptive statistics will be reported for each variable. To test whether there is a difference in conditions for each dependent variable, paired t-tests will be performed comparing the control post-tests to the intervention post-tests. Prior to statistical analysis, we will test the data for normality. If the data is not normally distributed, differences will be determined using the Wilcoxon Rank Sum test. Alpha will be set at 0.05.

Movement counts will be analysed using the Actilife 6 software (ActiGraph, Pensacola, FL). Each intervention session will be video recorded, and exploratory activity will also be coded from the recordings. Coding will be conducted using a momentary time sampling strategy from the videos of the first session of week 2 and week 6 (first exposure to the play environment in each condition) and the last session of week 4 and week 8 (last exposure to the play environment in each condition). Coding metrics will include physical activity, classified according to the Observational System for Recording Physical Activity in Children- Preschool version, social interactions, classified according to the Code for Active Student Participation and Engagement- Revised (CASPER-III), and object-related actions, classified by whether a child is touching, holding, or using a portable object with their hands using a categorical yes/no binary²⁸. Inter- and intra-rater reliability of at least 90% agreement will be established for each exploratory behavior on 10% of the video recordings using the ratio of [agreements/ (agreements + disagreements) X100] to establish a percentage of agreement.

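### Activity counts are collected in every play session, but the SAP's only test compares post-tests, which do not exist for this outcome, with no scaling for play time and no period term.

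*Protocol*

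**What the plan says.** Protocol, Dependent Measures, Aim 1: "Exploratory behavior expressed as activity counts during all intervention and control play sessions will be measured". The sensors go on the child's "right-side wrist and ankle and covered with wrist bands" and are "set to capture data in 1 second epochs".

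Protocol, Methods: each of the two blocks lasts three weeks (weeks 2-4 and 6-8). Three sessions per week is written only beside the control group.

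Protocol, Equipment: "children will play for up to 30 minutes within a 60-minute appointment". Breaks are allowed on listed criteria, one of which reads "there is a safety concern or harness slippage". A session ends at 30 minutes of exposure to the play environment or when the appointment ends. Time in the harness and PUMA is to be documented at each visit.

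SAP, Data Analysis: activity counts are one of four listed dependent variables. For each of them, "paired t-tests will be performed comparing the control post-tests to the intervention post-tests", with a rank test if the data are not normal. For the accelerometers the SAP adds only this: "Movement counts will be analysed using the Actilife 6 software". It also promises: "Descriptive statistics will be reported for each variable".

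The protocol uses the word post-test only for the standardized assessment in week 9, with week 5 as the midpoint. Both documents attach the choice of first and last sessions to video coding, not to the accelerometers.

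**The concern.** A paired t-test needs one value per child per condition. An outcome assessed once at the end of a block supplies that value directly. Activity counts do not: they are a series of sessions from two sensors, and the documents describe accelerometers only in play sessions, not at the week 5 or week 9 assessments. The SAP's contrast therefore has no defined input for this outcome. It names no session or summary, no sensor, and no total or per-minute scale.

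Two consequences go beyond missing detail. First, if totals were tested, a difference in play time between conditions would appear as a difference in exploration. Second, the two conditions lie four weeks apart (weeks 2-4 against weeks 6-8). Maturation and growing familiarity with the room can change activity whatever the harness does, and a plain paired test makes no allowance for that.

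**Working it through.** The documents give no sample size, power or effect size, so there is no stated figure to reproduce. The correlations, effect shapes, attendance and shortened play times below are assumptions.

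**1. How much data the outcome spans.**
- Sessions: 3 per week x 3 weeks = 9 per condition, and 9 x 2 = 18 per child. This assumes that the frequency stated for control also holds for the harness, and full attendance.
- Recordings: 18 sessions x 2 sensors = 36 per child.
- A full session holds 30 x 60 = 1,800 one-second epochs per sensor.
- A last-session test would use 2 of 18 sessions, or 2 of 12 if six are attended per condition.

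**2. What the SAP leaves open.** Last session or block mean, total or per minute, wrist or ankle: 2 x 2 x 2 = 8 combinations. The sensor factor is the weakest of the three, because both sensors can simply be reported.

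**3. Scale.** At an equal activity rate, the total changes by (minutes/30) - 1:
- 25 minutes: 25/30 - 1 = -17%
- 20 minutes: 20/30 - 1 = -33%

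Counts per minute of play are unchanged in both cases.

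**4. Period.** Let D be the harness effect and P the shift from period 1 to period 2, with no carry-over. Harness minus control is D - P in children who have the harness first (n1 of them) and D + P in those who have it second (n2).
- Paired mean difference: D + P(n2 - n1)/(n1 + n2). This is biased if the orders are unequal in size.
- With equal orders the bias is zero, but the spread of -P and +P adds about P² to the variance of the differences.
- Period 2 minus period 1 averages P - D in the first order and P + D in the second. Half the difference between them is D, so P cancels. Residual degrees of freedom fall from n - 1 to n - 2.

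**5. Mean or last session.** Take per-child, per-session condition differences with equal variance and equal correlation c. The variance of a mean of k sessions, relative to one session, is (1 + (k - 1)c)/k. For k = 9 and c = 0.4 this is (1 + 3.2)/9 = 0.467, so the last-session SE is 1/√0.467 = 1.46 times that of the mean. AR(1) columns use correlation decaying with the gap between sessions.

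| k = 9 | c = 0 | 0.2 | 0.4 | 0.6 | AR(1) 0.7 | AR(1) 0.8 |
|---|---|---|---|---|---|---|
| SE of last session / SE of mean | 3.00 | 1.86 | 1.46 | 1.25 | 1.50 | 1.32 |
| Effect/SE of mean relative to last session, linear growth from 0 | 1.50 | 0.93 | 0.73 | 0.62 | 0.75 | 0.66 |
| Same, plateau reached at session 4 | 2.33 | 1.45 | 1.14 | 0.97 | 1.17 | 1.03 |

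The first row also gives relative effect/SE when the effect is constant over sessions. Under linear growth the mean estimates half the final effect. Under the plateau (0, 1/3, 2/3, then 1 six times) it estimates 7/9 = 78% of it. With six sessions attended, the first row becomes 2.45, 1.73, 1.41, 1.22, 1.33 and 1.21.

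So the mean is more precise if the effect is steady, and has the lower effect/SE in five of the six settings if the effect builds linearly.

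**The case against.** The strongest reply is that nothing is discarded, because the plan does not say which session is tested. A reader might infer that post-test means the last session and that about eight of nine sessions per condition are thrown away. The documents do not support that: first-and-last selection is written for video only, and a block mean or total is equally compatible with the text. The SE ratios above therefore describe one hypothetical analysis under assumed correlations; they are not a loss in the plan. This objection stands.

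It is also fair that the mean is not plainly better. A harness effect may build over three weeks, and the mean would then dilute it. This stands too, and makes mean against last session a choice of estimand for the team.

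A reader might further infer that control play time goes unrecorded, since only harness and PUMA time is stated to be documented. That is too strong. The 30-minute exposure limit applies in both conditions, so someone must track it in control sessions. Nor need breaks shorten play, because they can be absorbed within the 60-minute appointment. What remains is that no matching control record is stated and that the SAP does not scale counts to play time.

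Finally, this is a pilot whose aims are all exploratory, and descriptive statistics are promised for every variable. That lowers the stakes. But the SAP sets alpha at 0.05 and plans a test for this variable, so what is tested should be defined.

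**Conclusion.** The concern holds as a mismatch between outcome and test. Activity counts are defined over all play sessions, while the only planned contrast is of post-tests that the documents do not define for accelerometers. Two improvements go beyond filling in detail: scaling to minutes of play, which removes play-time differences from the comparison, and a period term, which removes a shift between blocks that the plain paired test leaves as bias (unequal orders) or added variance (equal orders).

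The size cannot be fixed from the documents. The count of 2 of 18 sessions applies only on a last-session reading with three sessions per week in both conditions and full attendance. The 17% and 33% figures apply only if totals are used and play time differs by the assumed amounts. The period argument assumes no carry-over. Missing sensor detail alone would be a minor clarification. This is a change that should be made, and a cheap one. Video coding, GMFM and DMQ-18 are outside this point.

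**What to change.** For activity counts only, amend the SAP as follows.

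- Replace the post-test contrast with each child's mean count per minute of play over all attended sessions in each condition.
- Count only epochs within play time, which the one-second epochs allow. Log play start, stop and breaks the same way in both conditions.
- Report the last-session contrast, also per minute, beside the mean. The team chooses which is main and fixes this before data are seen.
- Analyse wrist and ankle separately.
- Compare conditions within child with a period term: compare the period 2 minus period 1 difference between the two orders.

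The cost is a few sentences of SAP text and one log kept in every session, with no new measurement of the child. There are two downsides. The period term uses one degree of freedom, in a pilot for which the documents give no sample size. The mean describes average rather than end-of-block behaviour and is diluted if the effect builds up, which is why the last-session contrast should be shown with it.
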